2.1.2. Handling Missing Data

In order to provide unbiased and informative findings, no replacement of missing values is planned for any parameters.

2.1.3. Descriptive Statistics in Summary Tables

- Continuous variables will be summarized using standard quantitative statistics: number of non-missing observations, mean, standard deviation, median, quartiles and range (minimum and maximum observed values). The number of missing observations will also be specified.

¹ 3M visit must occur after the final chemotherapy infusion in interval debulking patients. The 3M CT scan will serve as the baseline for assessing disease progression for purposes of device removal.

² 6M visit must occur after the final chemotherapy infusion in primary debulking patients. The 6M CT scan will serve as the baseline for assessing disease progression for purposes of device removal.

³ Peritoneal Carcinomatosis Index.

⁴ To be performed at time of device removal. Device removal may occur earlier if conditions for device removal described in Section 6.2 of the protocol are met.

	STATISTICAL ANALYSIS PLAN	MTRAP_SAP_v2.0_FINAL redacted.docx
		MTRAP Page 9/10

- *Categorical variables* will be summarized using classical frequency statistics: number of non-missing observations and percentages by categories. Percentages will be calculated on the number of non-missing observations, and will be displayed using one decimal. The number of missing observations will also be specified.

2.1.4. Inferential Analysis

- Confidence intervals:

The 95% bilateral confidence interval of the mean will be calculated for continuous variable if pertinent.

For categorical variables, if pertinent, the 95% asymptotic confidence interval will be calculated if theoretical assumptions are verified. If this is not the case, and the corresponding proportion is 0% or 100%, then the Agresti-Coull confidence interval will be calculated instead. In all other cases, the exact confidence interval will be calculated.

2.1.5. Interim Analysis

An interim analysis will be performed after all patients reach the 6-month time point to support the CE-marking application.

2.1.6. Data Listings

Patient data listings will be selected data supportive of summary statistical tables, including derived/calculated data from statistical process. These key data listings will be performed on selected analysis sets according to the focus of the listings.

2.2. Sample size calculation

The primary objective is to demonstrate that the safety of M-Trap, as measured by freedom from device- and procedure-related major adverse events (see Primary Endpoint for definition) through 6-months post-implantation, is non-inferior to historical controls. Using a success rate of 90% (freedom from device- and procedure-related major adverse events), a non-inferiority margin of 25%, >85% power, and one-sided alpha=0.05, a sample size of n=20 patients is needed to demonstrate that M-Trap is as safe as current standard-of-care through 6-months post-surgery. Assuming a 10% dropout rate, up to 22 patients will be treated to have 20 evaluable patients.

2.3. Analysis Sets

2.3.1. Definition of patient populations

Two (02) analysis sets populations will be defined:

- The Intent-to-Treat (ITT) population will comprise all patients who signed their informed consent, have been judged suitable for index procedure and are compliant with all inclusion/exclusion criteria.
- The As-Treated (AT) population will include all subjects from the ITT population implanted with at least one (1) M-Trap device.

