### **10.2. Analysis Sets**

In this study two analysis sets will be defined.

- The Intent-to-Treat (ITT) population will comprise all subjects who signed their informed consent, have been judged suitable for index procedure and are compliant with all inclusion/exclusion criteria.
- The As-Treated population will comprise all subjects from the ITT population implanted with at least one (1) M-Trap device.

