#### **11.3.1. Protocol Violations**

Protocol violations are defined as instances where the protocol requirements and/or regulatory guidelines were not followed and are generally more serious in nature. Protocol violations are considered to potentially affect the scientific soundness of the study and/or the rights, safety or welfare of subjects:

- Failure to obtain signed informed consent
- Unapproved (by sponsor and EC) investigator implanting the investigational device for the study purposes
- Subject inclusion/exclusion violations and protocol requirement violations that affect the primary endpoints of the study design

All protocol violations should be recorded by the Investigator in the appropriate page of the CRF, and documented by a Note to File by the investigator that can be filed in Site File.

Deviations will be reviewed and evaluated on an ongoing basis by the Sponsor and the Monitor. And, as necessary, appropriate corrective and preventive actions (including notification, center re-training, or discontinuation) will be put into place by the Sponsor and/or designee.

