2.4. Statistical Analyses

2.4.1. Patient Disposition and Follow-up

The number and percentage of patients included in each population and the reasons of non-inclusion in each subsequent population will be presented on the ITT population. The distribution of populations by site will be presented as well.

The number and percentage of patients present at each visit will be presented on the ITT and the As-treated population with the study exit reasons.

The average time of patient follow-up will be given on the ITT and on the As-treated population.

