2.4.5. Primary Analysis

Primary analysis of safety will be performed on the ITT population and the As-Treated populations.

The primary safety endpoint is freedom from device and procedure-related major adverse events through 6-months post-implantation, including shock, cardiac arrest, myocardial infarction, pulmonary embolism, prolonged intubation, unplanned reintubation, or adverse events leading to removal of the device, including infection, seroma formation, mesh migration, bowel obstruction, adhesions, and local cancer progression through the abdominal wall at M-Trap suture sites.

The primary safety endpoint will be analyzed using a unilateral one sample test for binomial proportion at the 5% level. In addition, the exact bilateral 95% confidence interval will also be given. The statistical test for the primary safety endpoint is given by:

- H0: M-Trap freedom MAE incidence \leq 90% - Non-inferiority margin (25%)
- Versus
- HA: M-Trap freedom MAE incidence $>$ 90% - Non-inferiority margin (25%)

A modified primary analysis will also be performed that uses a freedom from MAE incidence rate that is adjusted for the surgical complexity of the study population, as compared to the Patankar study population, which is the basis of the statistical rationale for this study (repeated in the table below). The total number of extended procedures will be split in four classes: 0, 1, 2, 3 and more.

Procedures	0	1	2	3 or more	AVG
Total patients	1352	1214	254	50	2870
Severe complications, n	51	92	44	9	196
Severe complications, %	3.8%	7.6%	17.3%	18.0%	6.8%

A further modified primary analysis will also be performed that only includes procedure-related events through 30 days, as this is the comparable population to the Patankar study population, which is the basis of the statistical rationale for this study.

Primary analysis of performance will be performed on the As-Treated population and by device location. This analysis will be also performed using these 3 following sub-populations: (1) platinum resistant, recurrent patients; (2) platinum sensitive, recurrent patients; (3) non-recurrent patients (see definition in part 2.5).

The primary performance endpoint is histopathologic evidence of tumor cell capture (see 2.5). Histopathology will be performed after device explant.

The primary performance endpoint will be assessed with exact one-sided 90% confidence intervals.

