2.4.6. Secondary analysis

Secondary analysis of safety will be performed on the ITT population and the As-Treated populations.

STATISTICAL ANALYSIS PLAN

Secondary safety endpoints include incidence of other device-related adverse events and all other adverse events long-term. Patients will be evaluated by physical examination, CT scan, ultrasound, and biomarker cancer antigen CA-125.

A medical coding will be done on the adverse events using the MedDRA dictionary. All adverse events (AEs) will be categorized by system organ class (SOC) and preferred term (PT). A complete description will be done for the following AEs:

- Total number of AEs/SAEs and corresponding number and percentage of patients
- Total number of device-related AEs/SAEs and corresponding number and percentage of patients
- Total number of unanticipated device-related AEs/SAEs and corresponding number and percentage of patients
- Total number of procedure-related AEs/SAEs and corresponding number and percentage of patients
- Total number of device deficiencies and corresponding number and percentage of patients
- The overall mortality rate will also be presented

Secondary analysis of performance will be performed on the As-Treated population.

Secondary performance endpoints include semi-quantitative scoring of disease focalization based on direct visual assessment, CT scan and ultrasound at the time of device removal. In addition, a microscopic assessment will be performed during explant, including cytological assessment of any ascites present, cytological assessment of peritoneal washings, if indicated, and a minimum of two (2) peritoneal biopsies from designated locations, if indicated.

The secondary performance endpoints are the percentages of recurrent patients with disease focalization scores of: 1) I, 2) I or II, 3) I, II or III, and 4) I, II, III or IV. This analysis will be also performed using the 3 sub-populations defined below ((1), (2), (3)), and using the populations (1) and (2) combined and overall.

The secondary performance endpoints will be assessed with exact one-sided 90% confidence intervals.

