2.5. Derived Criteria Calculation

If at least one of the items needed to calculate a derived criterion is missing then the corresponding derived criterion will be considered as missing.

- Derived criterion “ITT population” will be defined as follows:

If “Signed Informed Consent” = “Yes” and the date of signature of the consent form is filled and all inclusion/exclusion criteria are compliant and “Can the patient be treated with M-Trap” = “Yes” then “ITT population” = “YES”, else “ITT population” = “NO”.

- Derived criterion “As-Treated population” will be defined as follows:

If the date of signature of the consent form is filled and are compliant with all inclusion/exclusion criteria and “Can the patient be treated with M-Trap” = “Yes” and at least one device successfully implanted then “As-Treated population” = “YES”, else “As-Treated population” = “NO”.

- Derived criterion “Age at Enrollment” will be calculated as follows:

“Age at Enrollment” = “Date of signature of Informed Consent” – “Birth date” in years

- Derived criterion “Duration of patients Follow-up” will be calculated as follows:

“Duration of patients Follow-up” = “Last patient follow-up date” – “Procedure patient date”

If patient procedure date is missing Baseline/Screening date will be used (for ITT population)

- Derived criterion “Duration debulking surgery” will be calculated as follows:

“Duration debulking surgery” = “end time of debulking surgery” – “start time of debulking surgery”

- Derived criterion “Duration of implantation” will be calculated as follows:

“Duration of implantation” = “end time of implantation” – “start time of implantation”

- Derived criterion “Total number of procedures” will be equal to the number of checked boxes for “Extensive upper abdominal” and “Other procedures”.

- Derived criterion “Total number of extensive procedures” will be equal to the number of checked boxes for “Extensive upper abdominal”.

CRO will send to MTrap an Excel file with the list of all other surgical procedures to count their number.

- Derived criterion “Number of extended procedures (Patankar definition)” will be calculated as follows:

All patients start with a score of 1, since all patients had cytoreduction surgery.

Add 1 to the score if Pelvic or Para-aortic or Inguinal lymph node dissection are ticked or if any other procedure includes lymph node dissection (lymphadenectomy).

STATISTICAL ANALYSIS PLAN

Add 1 to the score if Small bowel resection is ticked.

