Table 55: Non-inferiority on Freedom of device and procedure related MAE through 6-months on AT population (Type 5)

Table 56: Freedom of device and procedure related MAE through 6-months on AT population using MAE expected incidence adjusted for the study population number of extended procedures (Patankar definition) (Type 8)

Table 57: Freedom of device and procedure related MAE through 30 days on AT population using MAE expected incidence adjusted for the study population number of extended procedures (Patankar definition) (Type 5)

Primary Performance analysis

Table 58: Histological evidence of tumor cell capture in at least one M-Trap device after device explant on AT population by device location (Type 2)

Table 59: Histological evidence of tumor cell capture in at least one M-Trap device after device explant on AT population with sub-analysis of histological evidence of tumor cell capture by device location and recurrence status (Type 2)

Secondary Analysis

Secondary Safety analysis

Table 60: AEs on ITT population (Type 6)

Table 61: AEs on AT population (Type 6)

Table 62: SAEs on ITT population (Type 6)

	STATISTICAL ANALYSIS PLAN	MTRAP_SAP_v2.0_FINAL redacted.docx
		MTRAP Page 19/20

Table 63: SAEs on AT population (Type 6)
 Table 64: M-trap device related AEs on ITT population (Type 6)
 Table 65: M-trap device related AEs on AT population (Type 6)
 Table 66: M-trap device related SAEs on ITT population (Type 6)
 Table 67: M-trap device related SAEs on AT population (Type 6)
 Table 68: Unanticipated M-trap device related AEs on ITT population (Type 6)
 Table 69: Unanticipated M-trap device related AEs on AT population (Type 6)
 Table 70: Unanticipated M-trap device related SAEs on ITT population (Type 6)
 Table 71: Unanticipated M-trap device related SAEs on AT population (Type 6)
 Table 72: M-trap procedure related AEs on ITT population (Type 6)
 Table 73: M-trap procedure related AEs on AT population (Type 6)
 Table 74: M-trap procedure related SAEs on ITT population (Type 6)
 Table 75: M-trap procedure related SAEs on AT population (Type 6)
 Table 76: Device deficiencies on ITT population (Type 5)
 Table 77: Device deficiencies on AT population (Type 5)
 Table 78: Mortality rate on ITT population (Type 5)
 Table 79: Mortality rate on AT population (Type 5)

Secondary performance analysis

Table 80: Disease focalization scores of I on AT population (Type 5)
 Table 81: Disease focalization scores of I or II on AT population (Type 5)

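### No analysis set holds every implanted patient: anyone implanted but recorded as ineligible drops out of the primary safety test and all adverse event and mortality tables

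*SAP*

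**What the plan says.** Protocol 10.2 and SAP 2.3.1 define two sets and no others. ITT takes consented patients who "have been judged suitable for index procedure and are compliant with all inclusion/exclusion criteria". The second set is nested in the first: "The As-Treated population will comprise all subjects from the ITT population implanted with at least one (1) M-Trap device".

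The derivation rules in SAP 2.5 repeat the eligibility condition for As-Treated, even where a device was successfully implanted: "If the date of signature of the consent form is filled and are compliant with all inclusion/exclusion criteria and", followed by the treatability and implantation conditions. Protocol 5.3.3 likewise counts a subject as treated only if she meets all eligibility criteria.

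Both levels of safety analysis use these sets. SAP 2.4.5 states "Primary analysis of safety will be performed on the ITT population and the As-Treated populations", and SAP 2.4.6 states "Secondary analysis of safety will be performed on the ITT population and the As-Treated populations". In SAP 4.1, Tables 55 to 57 (primary safety) are on As-Treated. Tables 60 to 79 (adverse events, serious adverse events, device deficiencies, mortality) are each on ITT or As-Treated.

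On disposition, SAP 2.4.1 says that "the reasons of non-inclusion in each subsequent population will be presented on the ITT population". Protocol 11.3.1 names among the protocol violations "Subject inclusion/exclusion violations and protocol requirement violations that affect the primary endpoints of the study design".

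**The concern.** A patient with an M-Trap in place is exposed to its risks whether or not a later check finds that she failed an entry criterion. The primary objective concerns device- and procedure-related major adverse events (MAEs) after implantation, so the natural denominator is everyone implanted. The plan has no such denominator.

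The gap is narrow but real. Eligibility is checked at screening and on the procedure day, and ineligibility found before or during the procedure makes the patient a screen failure (Protocol 5.3.2 and 6.1.1). What remains is a violation missed at both checks and recorded after implantation. The documents do not say what happens to that patient.

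The exclusion would also be hard to see in the planned tables. Reasons for non-inclusion are given on the ITT population, so the reason for not entering ITT is never tabulated. SAP 2.3.2 carries over the protocol's deviations section but not its violations section, and no table or listing title mentions eligibility violations.

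At stake are the non-inferiority conclusion and the reported event rates. The interim analysis at 6 months, meant to support CE-marking (Protocol 10.3, SAP 2.1.5), would draw on both.

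**Working it through.** **1. Set membership.** Take a patient who consented, was implanted with at least one device, and was later recorded as failing one criterion.

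- ITT: fails the eligibility condition (Protocol 10.2, SAP 2.3.1, SAP 2.5).
- As-Treated: fails because it is a subset of ITT, and again because the SAP 2.5 rule repeats the condition.
- Primary safety test and Tables 55 to 57: absent.
- Tables 60 to 79: absent.
- SAP 2.4.1 disposition summary: absent.

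**2. The plan's own sample size.** Inputs from SAP 2.2 and 2.4.5: expected success 90%, margin 25 points, so the null value is p0 = 0.90 - 0.25 = 0.65; one-sided 5% level; n = 20; power above 85%. The smallest count x with P(X >= x | n = 20, p0 = 0.65) <= 0.05 is 17. The exact level is 0.0444 and the power at 90% is 0.867. The stated n = 20 reproduces, and at most 3 of 20 patients may have an MAE.

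**3. Sensitivity to one or two patients.** The SAP does not say whether the binomial test is exact or asymptotic, so both are shown.

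- Exact: p = P(X >= x | n, 0.65).
- Normal: z = (x/n - 0.65) / sqrt(0.65 × 0.35 / n), no continuity correction.
- Worked case, 17/21: z = (0.8095 - 0.65) / 0.1041 = 1.533, p = 0.0627.
- Worked case, 17/20: z = (0.85 - 0.65) / 0.1067 = 1.875, p = 0.0304.

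The MAE counts below are assumptions.

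| Patients analysed | MAE-free / n | Exact p | Normal p |
|---|---|---|---|
| A: all 21 implanted, 4 MAEs | 17/21 | 0.0924 | 0.0627 |
| A: one ineligible patient with an MAE dropped | 17/20 | 0.0444 | 0.0304 |
| B: all 20 implanted, 3 MAEs | 17/20 | 0.0444 | 0.0304 |
| B: two event-free ineligible patients dropped | 15/18 | 0.0783 | 0.0515 |
| C: all 22 implanted, 4 MAEs | 18/22 | 0.0716 | 0.0491 |
| C: one ineligible patient with an MAE dropped | 18/21 | 0.0331 | 0.0233 |

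Case A turns a fail into a pass under either test, and the MAE rate falls from 4/21 = 19.0% to 3/20 = 15.0%. Case B turns a pass into a fail under either test. Case C reverses only under the exact test.

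**4. Most MAEs that still pass.**

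| n | Exact | Normal |
|---|---|---|
| 19 | 2 | 3 |
| 20 | 3 | 3 |
| 21 | 3 | 3 |
| 22 | 3 | 4 |

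**5. A separate mismatch.** SAP 2.4.5 requires the primary safety analysis on ITT and As-Treated, but Table 55 is titled "Non-inferiority on Freedom of device and procedure related MAE through 6-months on AT population", and Tables 56 and 57 are also on As-Treated only. No ITT version is listed. This does not depend on the eligibility question and adds nothing to its weight.

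**The case against.** The strongest reply is that the case may never occur. Two eligibility checks and a treatability field precede implantation, and the SAP does not say that a violation found later would change the compliance data behind the set flags. If the day-0 assessment stood, the patient would stay in both sets. This stands as a limit on likelihood. It is not a defence of the rule, which leaves her membership to an unstated convention.

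The reversals are also boundary cases. Suppose the true success rate is 90% and exactly one patient, chosen at random, is ineligible among 20, 21 or 22 implanted. The chance that dropping her turns a fail into a pass is then 0% to 2.0%, depending on n and the test. The chance of the opposite change is 0% to 16%, and that direction works against the sponsor. These figures are right under those assumptions. They would differ if the true event rate were higher or if ineligible patients were at greater risk.

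Nor would she be invisible. Adverse events are reported whatever the analysis set and reviewed by the sponsor and the DSMB (Protocol 7.1.2 and 8.4). Violations are recorded in the CRF and go into progress reports to the authority and ethics committee where applicable (Protocol 11.3). SAP 2.1.6 leaves the listing populations open, so a listing might show her. All of this is true, but none of it puts her into the test or the event rates.

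Finally, an all-implanted sensitivity analysis would close the reporting gap without changing the primary population. That is a workable lesser remedy. It would still leave the primary safety claim resting on a selected subset of those exposed.

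**Conclusion.** The concern holds. As written, the plan drops an implanted patient recorded as ineligible from the primary safety test and from all adverse event, serious adverse event and mortality tables. Confidence in this reading is high, because the definitions, derivation rules and table titles agree.

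The numerical effect is conditional. It requires at least one such patient, and the documents give no expected number. The direction of bias is open. When the count lies near the threshold, one exclusion can reverse the conclusion in the sponsor's favour (17/21 to 17/20), and two event-free exclusions can reverse it the other way (17/20 to 15/18), under either form of the test. The point should be fixed before analysis; it does not undermine the design.

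**What to change.** Define a Safety set: all consented patients with at least one M-Trap device implanted, regardless of eligibility compliance, with time counted from implantation. Use it for the primary safety test (Tables 55 to 57) and for the adverse event, serious adverse event and mortality tables. Keep the eligibility-compliant ITT and As-Treated sets as sensitivity analyses.

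Start the disposition account in SAP 2.4.1 from all implanted patients and list each eligibility violation. Align SAP 2.3.1, 2.4.1 and 2.5 with Protocol 5.3.3 and 10.2.

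Separately, add ITT versions of Tables 55 to 57 to match SAP 2.4.5. These would also cover eligible patients whose implantation failed.

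The cost is SAP wording and table programming, with ethics committee re-approval for the protocol text (Protocol 11.2). No new assessments should be needed: Protocol 6.2.3 follows all patients through 18 months. Protocol 5.3.3, however, ties follow-up to eligible treated subjects, so its wording should be aligned. If no such patient occurs, the As-Treated results do not change. If one does, the reported MAE rate may move up or down.
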